10.2.1.2. Phase 2 Analysis of Primary Objective

The primary analysis will test the null hypothesis that the median PFS is equal to 4.6 months. The time-to-event distribution for PFS will be estimated using the Kaplan-Meier method and the analysis will be based on the two-sided 90% confidence interval for the median (equivalent to the use of a one-sided test at the $\alpha=0.05$ level of significance).

Additional exploratory analyses of PFS will be conducted in subgroups defined based on number of prior therapies (one versus two or more), histology, and endoglin expression on sarcoma tissue.

For the angiosarcoma cohorts, the overall response rate and median duration of response by RECIST 1.1 will be calculated and the response rate will include the two-sided 90% confidence interval.

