3.2.2. Primary objectives

- To estimate the PFS of patients with advanced soft tissue sarcoma by RECIST 1.1
- To estimate the ORR in a cohort of patients with angiosarcoma by RECIST 1.1

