5.3.5.2 Clinical Protocol

Table 6: Schedule of Assessments Phase 2 Soft Tissue Sarcoma

Protocol Activities	Screening	Cycle 1 [23]					Cycle 2+ [21] [23]				End of Study [3]	28 Day Follow-up [22]
	Day -28	Day 1 [1]	Day 4 [1]	Day 8 [1]	Day 15 [1]	Day 22 [1]	Day 1 [1]	Day 8 [1]	Day 15 [1]	Day 22 [1]		
Baseline Documentation												
Informed Consent [4]	X											
Medical/Oncology History [5]	X											
Baseline Signs and Symptoms [5]	X											
Physical Examination [6]	X	X					X				X	
Vital Signs [7]	X	X	X	X	X	X	X	X	X	X	X	
Laboratory Studies												
Hematology [8]	X+Fe	X+Fe			X		X		X		X	
Coagulation [8]	X	X										
Blood Chemistry [8]	X+TSH	X+TSH			X		X + TSH				X + TSH	
Pregnancy Test [9]	X	X										X
Urinalysis [10]	X	X					X				X	
Treatment w/ Study Drug												
TRC105 Dosing [11]		X Split	X Split	X	X	X	X	X	X	X		
Pazopanib [12]		X Daily										
Tumor Assessments												
CT or MRI Scans [13]	X									Even Cycles	X	
Other Clinical Assessments												
12-Lead ECG [14]	X	X			X						X	
Concomitant Medications/Treatments [15]	X	X	X	X	X	X	X	X	X	X	X	X
Adverse Events [16]		X	X	X	X	X	X	X	X	X	X	X
Special Laboratory Assessments												
Anti-Product Antibody [17]		X					Even Cycles				X	X
Trough PK [18]		X					Even Cycles				X	X
Protein Biomarkers [19]		X					Even Cycles				X	
Archival Tumor Tissue [20]	X											

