13. **CT or MRI Tumor Imaging:** Images of the chest, abdomen, and pelvis to be performed at screening, and on-study as outlined in the assessment table. Known areas of disease should be consistently followed throughout the study. Assessments should be performed whenever disease progression is suspected. Allowable window for tumor imaging studies is +/- 7 days. Brain and bone scans are to be performed if metastases are suspected at screening or during study therapy. Color photography with caliper or ruler measurements, when possible, should be used to assess cutaneous tumors (target lesions).

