5.3.5.2 Clinical Protocol

7. ASSESSMENT OF EFFICACY

7.1. Radiological Tumor Assessment

The primary efficacy endpoint for phase 2 is PFS, defined as time from screening to either first disease progression or death from any cause per RECIST version 1.1 [68]. Patients alive at the time of analysis will be censored at the date of last disease assessment.

The primary efficacy assessment will be best overall response as defined in Section 7.1.2. The determination of antitumor efficacy will be based on objective tumor assessments made by the Investigator according to RECIST version 1.1 [68]. Investigators will make treatment decisions based on these assessments. All lesions will be classified as target or non-target lesions at the Screening visit. Each lesion designation will be maintained through the course of the study.

The same method and technique should be used to characterize each identified and reported lesion at Screening, during the study treatment period, and at the End of Study visit. Imaging-based evaluation over clinical examination is the required technique when both could be used to assess the antitumor effect of the treatment. Clinical Oncology review of all tumor measurements is desired.

Whenever possible, clinical evaluation of superficial lesions should not be used as the sole form of measurement. However, when necessary, color photograph with metric caliper is acceptable. Tumor evaluation by positron emission tomography (PET) scan or by ultrasound may not substitute for CT or MRI scans.

Radiological tumor assessments will be performed at screening, as outlined in the Schedule of Assessments (Table 4, Table 5, Table 6 and Table 7), and whenever disease progression is suspected. Another tumor assessment will be performed at the End of Study Visit if an assessment has not been performed within the prior 8 weeks. All patient files and radiological images must be available for CRF source verification.

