10.1.2. Phase 2 Statistical Design/Sample Size

Sixty three patients will be treated in the phase 2 portion of the study.

The study population for safety and efficacy will include all patients receiving at least a portion of one dose of TRC105.

Assuming a true median PFS of 4.6 months, a 9-month accrual period, a 6-month follow-up period, and based on the use of a one-sided test at the $\alpha=0.05$ level of significance, a sample size of 63 patients will provide 86% power to detect a 50% increase in the median PFS (i.e., a median of 6.9 months). These power estimates are based on the approach of Lawless [1].

Two additional phase 2 cohorts of up to 13 patients each with angiosarcoma will be enrolled into separate cohorts, angiosarcoma cohort 1 and 2. Angiosarcoma cohort 1: Assuming a 15% response rate by RECIST with pazopanib alone, 5 responders with TRC105 alone or in combination with pazopanib will provide >90% confidence the true response rate is >15% (two-sided exact 90% binomial with 5 of 13 responders is 16.57 and 64.52%). Angiosarcoma cohort 2: Assuming a 15% response rate by RECIST with pazopanib alone, 5 responders with TRC105 in combination with pazopanib will provide >90% confidence that the true response rate is >15%.

For each of the angiosarcoma cohorts, the two-sided exact 90% binomial with 5 of 13 responders is 16.57% and 64.52%.

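### The stated 86% power belongs to a parametric exponential test; the planned Kaplan-Meier median rule has about 63% (log-log interval) or 72% (linear interval) under the same inputs, and the interval is not named

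*Combined protocol and SAP*

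**What the plan says.** Section 10.2.1.2 sets the null median PFS at 4.6 months. The PFS distribution is to be "estimated using the Kaplan-Meier method and the analysis will be based on the two-sided 90% confidence interval for the median", and this is described as "equivalent to the use of a one-sided test at the" 0.05 level. The synopsis repeats the rule. Neither place says how the interval is built (linear, log-log or another form).

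Section 10.1.2 takes 9 months of accrual and 6 months of follow-up, and states that "a sample size of 63 patients will provide 86% power to detect a 50% increase in the median PFS", to 6.9 months. It adds: "These power estimates are based on the approach of Lawless [1", citing a textbook on lifetime data. The synopsis gives the same 86% without the source. No dropout rate is given, and no power figure is given for the Kaplan-Meier rule.

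Three other places bear on the point:

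- Section 3.2.2 words the objective as estimation: "To estimate the PFS of patients with advanced soft tissue sarcoma by RECIST 1.1".
- Section 7.1 has PFS "defined as time from screening to either first disease progression or death from any cause per RECIST version 1.1".
- Table 6, "Schedule of Assessments Phase 2 Soft Tissue Sarcoma", puts routine scans on day 22 of even cycles. Its imaging footnote adds: "Assessments should be performed whenever disease progression is suspected".

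**The concern.** A power statement is useful only if it describes the test that will be run. A parametric exponential test draws on every event over the whole 15 months. A Kaplan-Meier interval for the median, compared with 4.6 months, draws only on the survival estimate around 4.6 months and so uses much less information. A reader will take 86% as the chance that the primary analysis detects a 6.9-month median. If the real chance is well below that, a null result will be over-read as evidence against the combination.

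The second issue is the claimed equivalence to a one-sided 5% test. At 63 patients the interval constructions differ in both error rate and power. If the form is not named in advance, that choice is open after the data are seen.

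**Working it through.** **Inputs.** From sections 10.1.2 and 10.2.1.2: N = 63, medians 4.6 and 6.9 months, accrual 9 months, follow-up 6 months, one-sided alpha 0.05. Assumed, because the plan is silent: uniform accrual, no dropout, and progression observed when it occurs. Exponential PFS is also assumed. The documents never use that word; it is inferred from the match in step 1.

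**1. Reproducing the 86%.** With hazard λ = ln 2 / median, the probability of an observed event is 1 − (e^(−6λ) − e^(−15λ)) / (9λ).

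- Median 4.6: λ = 0.1507, probability 0.778, expected events 63 × 0.778 = 49.04.
- Median 6.9: λ = 0.1005, probability 0.640, expected events 63 × 0.640 = 40.30.

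Power on the log-hazard scale, with null variance for the critical value and alternative variance for the power:

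Φ((ln 1.5 − 1.645/√49.04) × √40.30) = Φ((0.4055 − 0.2349) × 6.349) = Φ(1.083) = 0.861.

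This is the plan's 86%. Neighbouring parametric forms give similar values, for example 0.824 with the alternative variance only and 0.884 with the null variance only.

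**2. The planned rule.** Every patient has at least 6 months of follow-up, which is longer than 4.6 months. Without dropout, the Kaplan-Meier estimate at 4.6 months is therefore X/63, where X is the number progression-free at that time. The lower limit for the median exceeds 4.6 months when the lower 90% limit for S(4.6) exceeds 0.5.

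| X of 63 | Linear lower limit | Log-log lower limit |
|---|---|---|
| 38 | 0.502 | 0.494 |
| 39 | 0.518 | 0.510 |

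The linear interval therefore needs at least 38 progression-free patients, and the log-log interval at least 39.

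**3. Power and error of that rule.** Under the null S(4.6) = 0.5. With a 6.9-month exponential median, S(4.6) = 0.5^(4.6/6.9) = 0.630. Exact binomial tails:

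| Interval | Needs | One-sided error | Power | Chance of missing 6.9 months |
|---|---|---|---|---|
| Log-log | ≥ 39 | 0.038 | 0.625 | 37% |
| Linear | ≥ 38 | 0.065 | 0.718 | 28% |
| As stated in the plan | – | 0.05 | 0.86 | 14% |

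Simulating the full Kaplan-Meier procedure gave 0.626 and 0.717 for power (40,000 trials). Extending follow-up to 9 months left power at about 63% and 72%, because the rule looks only at S(4.6).

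**4. Sensitivity to shape and dropout.** For an assumed Weibull shape k, S(4.6) = 0.5^((4.6/6.9)^k).

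| Assumption | Log-log power | Linear power |
|---|---|---|
| Shape 0.8 (S = 0.606) | 0.470 | 0.572 |
| Shape 1.0 (S = 0.630) | 0.625 | 0.718 |
| Shape 1.2 (S = 0.653) | 0.760 | 0.833 |
| Exponential, 10% dropout by 4.6 months | 0.615 | 0.663 |
| Exponential, 20% dropout by 4.6 months | 0.586 | 0.638 |

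The null error does not depend on the shape, because S(4.6) = 0.5 whenever the median is 4.6 months.

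**5. Scan timing.** Day 22 of cycles 2, 4 and 6 is study day 50, 106 and 162 (28 × (cycle − 1) + 22), or about 1.6, 3.5 and 5.3 months. The 4.6-month point is day 140, so no routine scan falls there.

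**The case against.** The strongest reply is that 63% is also an idealised figure, because it assumes progression is seen as soon as it happens. The real schedule departs from that in three ways: 8-weekly scans, a window of 7 days either side, and a clock that starts at screening, up to 28 days before treatment. For the 39-of-63 rule, treating 4.6 months as the true underlying median:

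| Setting | Power | One-sided error |
|---|---|---|
| Progression seen only at scans, timed from cycle 1 day 1 | about 95% | about 38% |
| Half of progressions caught at once by unscheduled scans | about 82% | about 15% |
| Continuous observation, clock started 0 to 28 days before treatment | about 80% | about 12% |
| Seen only at scans, clock started 28 days before treatment | about 70% | about 6% |

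On this view the larger hazard may be a false positive, and no interval construction can be said to hold 5% without qualification. If the 4.6-month benchmark was itself dated by scans, these errors would be smaller; the documents do not say.

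Much of this stands. The 63% and the 5% control of the log-log interval must both be read as conditional on continuous observation. It does not rescue the 86%, whose reproduction in step 1 rests on the same idealisation, and none of these settings gives 86% power at 5% error.

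Two smaller points are fair. The exponential basis is inferred from a numerical match, because the cited text is not available here. But none of the parametric variants is the planned rule, so the mismatch does not depend on which one was used. And this is a single-arm phase 2a cohort with an estimation objective. Section 10.2.1.2 nevertheless sets a null hypothesis, and section 10.1.2 attaches power to it.

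**Conclusion.** The concern holds. The 86% is arithmetically sound for an exponential test on all events but is not the power of the planned analysis. Assuming exponential PFS, uniform accrual, no dropout and continuously observed progression, the planned rule has 62.5% power with a log-log interval and 71.8% with a linear one. The shortfall is about 24 or 14 percentage points. Weibull shapes from 0.8 to 1.2 move these to 47–76% and 57–83%, all below 86%.

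The claimed equivalence to a one-sided 5% test also depends on a choice the plan leaves open: one patient, 38 against 39, separates an error of 6.5% from one of 3.8%. The Kaplan-Meier estimate and its interval remain usable for the stated objective. The plan should be corrected, but the analysis is not invalidated.

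**What to change.** Keep the Kaplan-Meier 90% interval as the primary analysis. In section 10.2.1.2 and the synopsis, name a construction that keeps the one-sided error within 5% under continuous observation, for example log-log. In section 10.1.2 and the synopsis, replace the 86% sentence with wording such as:

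> With 63 patients the Kaplan-Meier 90% CI (log-log) has about 63% power to exclude 4.6 months if the true median is 6.9 months, assuming exponential PFS, 9-month uniform accrual, 6-month follow-up, no dropout and continuously observed progression (about 47% to 76% for Weibull shapes 0.8 to 1.2).

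The continuous-observation condition must stay in that sentence. Simulated power and error under the Table 6 scan days and the screening time origin would be a useful addition.

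A one-sample exponential or log-rank test against hazard ln 2/4.6 should be added only as a labelled supportive analysis, with a statement that its error depends on the PFS shape. In simulation with a true median of 4.6 months, the log-rank version had a one-sided error of 0.150 at Weibull shape 0.8, 0.043 at 1.0 and 0.007 at 1.2, so it is not a safe replacement for the primary test.

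The cost is wording in section 10 and the synopsis, with no extra patients and no change of primary test. The price is a less favourable stated power, and a log-log interval that is slightly conservative (about 4%).

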10.2.2. Analysis of Pharmacokinetics

Peak and trough serum TRC105 concentrations will be measured using validated ELISA methods. The TRC105 pharmacokinetic data will be assessed for potential correlations with response, PFS, survival, adverse events, and baseline characteristics using descriptive statistics and models as appropriate.

5.3.5.2 Clinical Protocol**10.2.3. Objective Response**

The best response (CR, PR, SD or PD according to RECIST 1.1) for each patient with measurable disease who received at least one dose of TRC105 study drug will be listed by cohort. Stable disease will be defined as lack of tumor progression lasting for 2 cycles or longer.

10.2.4. Analysis of Protein Biomarkers

Angiogenic protein biomarker data for each patient who received at least one dose of TRC105 study drug will be listed.

10.2.5. Analysis of Immunogenicity

Anti-product antibody concentrations will be measured using validated ELISA methods at the timepoints specified in the Schedule of Assessments ([Table 4](#), [Table 5](#), [Table 6](#) and [Table 7](#)). Anti-product antibody concentrations will be evaluated in the context of pharmacokinetic parameters and AE profiles.

10.2.6. Analysis of Archival Tumor Tissue

Endoglin expression within the tumor vasculature and on sarcoma tissue will be quantified for each patient who received at least one dose of TRC105 study drug and will be listed by histologic type of soft tissue sarcoma. Expression will be determined by immunohistochemistry (IHC). Other markers that may relate to efficacy or toxicity of TRC105 may also be explored.

5.3.5.2 Clinical Protocol**11. DIRECT ACCESS TO SOURCE DATA/DOCUMENTS**

All data entered on CRFs/eCRFs must be verifiable within the patients' source documents (written or electronic record). The Investigator /institution guarantees TRACON representatives and appropriate regulatory authorities direct access to the original source records for the duration of the agreed study record retention period. Printouts of source records that are electronically obtained and stored will not be acceptable for audit/inspection unless provided as certified exact copies and the data remains as meaningful and useful as in its original electronic state.

Legally protected subject identification and other personal health information must be securely stored with limited access by the participating institutions. Unless secure provisions are established by the institution to allow TRACON (or designee) to perform remote monitoring of electronic source records, TRACON (or designee) will review source records/data on site and will not remove any such protected health information.

5.3.5.2 Clinical Protocol**12. QUALITY CONTROL AND QUALITY ASSURANCE**

Monitoring visits to clinical investigator sites will be made by TRACON or its representatives periodically during the trial to ensure that GCPs and all aspects of the protocol are being followed.

The trial site will also be subject to possible inspection by the institutional review board (IRB) or independent ethics committee (IEC) or other appropriate regulatory authority. The trial site is also subject to quality assurance audits performed by TRACON or its representatives.

It is important that the Investigator(s) and their relevant personnel are available during the monitoring visits, audits, and inspections and that sufficient attention, time, and support is devoted to the process.

TRACON and its representatives will be governed by applicable regulations, good clinical practice standards, and internal SOPs for the conduct of monitoring visits and QA audits.

5.3.5.2 Clinical Protocol**13. ETHICS****13.1. Institutional Review Board (IRB)/Independent Ethics Committee (IEC)**

It is the responsibility of the Investigator to have approval of the trial protocol, protocol amendments, informed consent forms, and advertisements from the IRB/IEC before potential patients are consented for participation on the trial. All correspondence and other evidence of appropriate and timely communications with the IRB/IEC should be retained in the Investigator/site files. Copies of all IRB/IEC approvals should also be forwarded to TRACON.

The only circumstance in which an amendment may be initiated prior to IRB/IEC approval is where the change is necessary to eliminate apparent immediate hazards to the patients. In that event, the Investigator must notify the IRB/IEC and TRACON in writing within 5 business days after the implementation.

13.2. Ethical Conduct of the Study

The trial will be performed in accordance with the protocol, applicable local regulatory requirements and laws, and the International Conference on Harmonization Guideline on Good Clinical Practice, which supports the application of ethical principles that have their origin in the Declaration of Helsinki (see ICH E6, § 2.1).

13.3. Written Informed Consent

The informed consent form language must be agreed upon by TRACON and the IRB/IEC and must be in compliance with ICH GCP, local regulatory requirements, and legal requirements. The informed consent information must not be changed without prior approval by TRACON and the IRB/IEC. The informed consent form used in this trial, and any changes made during the course of the trial, must be approved by both the IRB/IEC and TRACON, or designee, before use.

It is the responsibility of the Investigator to give each patient full and adequate verbal and written information regarding the objective and procedures of the trial and the possible risks involved. This information must be provided to the patient prior to undertaking any trial-related procedure. Patients must be informed about their right to withdraw from the trial at any time. Furthermore, it is the responsibility of the Investigator to ensure all patients are appropriately informed before obtaining their signed and dated consent. Signatures from the investigator conducting the informed consent discussion should also be obtained, prior to undertaking any trial-related procedure. Consent by a legally authorized representative is not permitted. Should an impartial witness be needed, ICH E6 requirements for impartial witnesses will apply.

The Investigator will retain the original of each patient's signed consent form in the Investigator/site files.

13.4. Patient Compensation

Patients will not be compensated for participation in this trial; this will be outlined in the patient informed consent form.

5.3.5.2 Clinical Protocol**14. DATA HANDLING AND RECORDKEEPING****14.1. Inspection of Records**

CRF's are required and should be completed for each patient who receives treatment with pazopanib or TRC105. Screen failure CRF's will not be collected. Nevertheless, records of potential patients identified and screened shall be retained on site screening logs. The completed original CRFs are the sole property of TRACON and should not be made available in any form to third parties without written permission from TRACON (except for authorized representatives of the HRA and in accordance with HIPAA regulations).

It is the Investigator's responsibility to ensure completion and to review and approve all CRF data. The investigator will sign off on his/her data per patient. These signatures serve to attest that the investigator has reviewed and approved the information contained on the case report forms and that the information is complete, accurate, and true. At all times, the Investigator has final personal responsibility for the accuracy and authenticity of all clinical and laboratory data entered on the CRFs.

The use of electronic CRFs (eCRFs) to capture study data using automated computerized data capture systems does not change the principles and requirements for collecting study data. The investigator still retains final personal responsibility for eCRF data and any associated data pertaining to it (e.g. metadata including any record of change to the originally recorded data). The investigator's signed approval of the eCRF data serves to attest that the electronic data and all of its associated metadata (including changes) has been reviewed and accepted as complete, accurate, and true for each patient in the study.

